Primary: Disease control rate at 24 weeks after initiation of tamoxifen (since day 1 cycle 1), defined by absence of radiological progression in conventional imaging

examinations by RECIST 1.1 (Appendix I). Isolated increase of biomarker (chromogranin A) or specific hormone will not be considered progression.

Secondary:

(1) Progression-free survival, defined by time from tamoxifen day 1 cycle 1 to death from any cause or radiological progression by RECIST 1.1, whichever occurs first. Patients alive and without progression at the time of study analysis will be censored for time-to-event analysis.

(2) Biochemical response will be defined by at least 30 percent drop in the marker (chromogranin and / or specific hormone) at any time of treatment in relation to pre-treatment value (s).

(3) Radiological response rate by RECIST criteria 1.1 during the study period.

(4) Disease control rate, defined by absence of radiological progression by RECIST 1.1 criteria, according to the intensity of expression by immunohistochemistry (IHC) of HR and also according to primary site (pancreas, gastrointestinal or lung) during the study period.

(5) Toxicities frequency: Adverse events of grades 2 or more by Common Adverse Event Toxicity Criteria (CTCAE) version 5.0 during the study period.

Exploratory:

(1) Evaluate possible variations in intensity and number of sites between PET-CT gallium-68 pre-treatment and 12 weeks after initiation of tamoxifen as a continuous variable for each capture lesion. Although this examination is part of the evaluation routine of NET, in this study we will evaluate differences in the intensity of uptake with tamoxifen.

(2) Evaluate the percentage of CTC positivity in NET, as well as average number of cells in case of positivity. To evaluate the presence of estrogen and progesterone receptors in CTC.

Methodology:

Study design:

A single-arm, unicentric, single-stage clinical study of tamoxifen for patients with well differentiated neuroendocrine tumors and radiological progression with positive (> 1 percent) HR (estrogen and / or progesterone) expression by IHC.

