Patients eligible for the clinical and radiological criteria and signing the Informed Consent Form (ICF) will have the biopsy material (tumor stored in paraffin) evaluated for IHC of HR. If the expression is positive, eligibility will be complete and patients will receive tamoxifen continuously until radiological progression by RECIST 1.1, unacceptable toxicity or withdrawal of consent. If the expression for HR is negative, the patient will be informed of their ineligibility for this study and will continue to be treated by the Clinical Oncology team without any detriment to their care.

Patients will be followed up by the study team for assessments of:

(1) Safety: first in 3 weeks after tamoxifen day 1 cycle 1, and then every 6 weeks from tamoxifen day 1 cycle 1 for anamnesis with active questioning of disease symptoms and possible adverse events, physical examination and routine laboratory routine (hemogram, biochemistry, liver and renal function);

(2) Efficacy: patients will perform imaging (chest, abdomen and pelvic tomography or abdominal and pelvic resonance imaging) at baseline or pre-treatment and every 12 weeks until progression or intolerance / exit from the study. The image response evaluations will be through RECIST 1.1. For evaluation of the biochemical response, patients will undergo hormonal dosing with serum chromogranin A and specific hormones in cases of functioning NET (eg 5-HIAA dosing in 24-hour urine) at the baseline and every 12 weeks until progression (increased chromogranin and / or the functioning hormone will not be characterized as disease progression if imaging shows progression).

(3) Exploratory assessment: Patients will be assessed for somatostatin receptor expressiveness by the functional examination of PET-CT Gallium-68, which will be performed before treatment and at week 12. This evaluation, because it is exploratory, does not will be part of the definition of disease progression.

Also as an exploratory analysis, a blood sample will be collected to search for circulating tumor cells at the baseline visit (a collection only).

After a period of one year, the consultations laboratory and imaging examinations will be performed every 12 weeks until the disease progresses. Collection and evaluation times are summarized in the Table of Procedures (TABLE 1).

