If there is no CTCAE 5.0 classification for an adverse event, the severity degree of mild, moderate, severe and life threatening will be used. Adverse event monitoring will be performed at Week 3 after initiation of treatment (window - / + 3 days) and at each return with the oncologist every 6 weeks (window - / + 3 days). Monitoring of adverse events should be continued for at least 4 weeks after the last dose of study treatment.

An adverse event for the purposes of this protocol is the appearance of (or worsening of the pre-existing) signal (s), symptom (s) or undesirable medical condition (s) occurring after signature of free and informed consent, even if the event is not considered to be related to the study drug (s). The occurrence of adverse events should be obtained through indirect questions asked to the patient at each visit during the study. Adverse events may also be detected when reported voluntarily by the patient during or between visits or by physical examination, laboratory examination or other evaluation.

Whenever possible, each adverse event should be evaluated to determine:

1. Severity (mild, moderate, severe and life threatening) or (CTCAE grade 5.0)
2. Their relationship to each study drug (suspected / suspected)
3. Their duration (starting dates and final or continuing in the final exam)
4. Conduct adopted (no dosage adopted, dosage of study drug adjusted / temporarily discontinued, study drug permanently discontinued as a result of said adverse event, concomitant medication given, non-medicated therapy, prolonged hospitalization / hospitalization).

Patients requiring hospitalization should be immediately identified by the study investigators who monitor all patients.

Treatment suspension criteria:

Patients can discontinue study treatment for one or more of the following reasons:

- Progression of the disease (documented by images and defined by RECIST 1.1 criteria)

Clinical progression, based on the evaluation of the investigator

- Death.
- Adverse event
- Withdrawal of consent by the patient.
- Need for new cancer therapy and / or surgery.

Efficacy and Follow-Up Assessment

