Descriptive statistics will be used to report the results of categorical and continuous variables. The time-to-event variables will be reported in medians and Kaplan Meyer curves. The degrees of toxicity will be tabulated. The number of patients discontinuing treatment due to toxicity will be presented.

Efficacy and toxicity analyzes will be performed by intention to treat. Patients receiving at least one dose of tamoxifen will be evaluated for toxicity and efficacy.

Inferential analyzes of the primary outcome according to primary site and IHC HR expression intensity will be conducted to depend on the number of cases per subgroup; if possible, these analyzes will be performed with the chi-square test. The analyzes of intensity of uptake intensity to PET-CT gallium-68 will be with paired T-test. The CTC analysis will be presented in a descriptive way.

Sample Size Calculation

To calculate the sample size, we considered the disease control rate H0 at 6 months of 50 percent (placebo arm result of the phase III studies) 5,23 and H1 as a 6 months disease control rate of 70 percent. A 10 percent bitailed type I error was considered, 80 percent power loss and 30 percent follow up loss. With these calculations, the sample number will be 22 patients.

Recruitment and Study Duration

At the AC Camargo Cancer Center, 30 patients with advanced NET are treated annually. Therefore, considering the patients already under treatment and the possible candidates without previous treatment and that out of every 10 patients, N = 4 will meet eligibility criteria (NETs with positive HR), we estimate to recruit the study population in a maximum period of 3 years and have the first full evaluation in 3 ½ years.

Ethical Considerations

The study will be conducted in accordance with the protocol, Good Clinical Practice guidelines of the International Conference on Harmonization (ICH GCP) and applicable local laws and regulatory requirements. The Free and Informed Consent Term (ICF) must be in accordance with ICH GCP guidelines, local regulatory regulations, and legal requirements. See Appendix 2 for ICF.

The investigator should ensure that each study patient, or his / her legal representative, is fully informed about the nature and objectives of the study and

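### The week-24 disease control endpoint scores an early death without RECIST progression as controlled and gives no status to a treated patient without a week-24 scan; with 22 patients, one or two such cases can reverse the result

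*Combined protocol and SAP*

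**What the plan says.** **Endpoint.** Under Outcomes, the primary endpoint is "Disease control rate at 24 weeks after initiation of tamoxifen (since day 1 cycle 1), defined by absence of radiological progression in conventional imaging". Progression is judged by RECIST 1.1, as set out in Appendix 1. The only rule added there is that a rise in a marker or hormone alone is not progression. Death is not mentioned. In the same section, progression-free survival (PFS) counts death from any cause as an event.

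**Analysis set.** The Statistical plan specifies intention to treat and adds: "Patients receiving at least one dose of tamoxifen will be evaluated for toxicity and efficacy". Appendix 1 instead assigns response categories to patients with at least one cycle of tamoxifen. The Administration section defines a cycle as 42 days.

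**Stopping and imaging.** The Treatment suspension criteria include death, "Clinical progression, based on the evaluation of the investigator" and "Need for new cancer therapy and / or surgery". Under Study design, imaging runs "every 12 weeks until progression or intolerance / exit from the study". The Efficacy and Follow-Up Assessment section lets patients with clinical but not radiological progression stop tamoxifen and go on being imaged until progression. If they start new treatment, PFS is censored at the last tamoxifen date. The note that ends Appendix 1 asks that every effort be made to document objective progression after treatment stops.

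**Test.** The Sample Size Calculation says "we considered the disease control rate H0 at 6 months of 50 percent (placebo arm result of the phase III studies"), takes 70% as the alternative, and continues: "A 10 percent bitailed type I error was considered, 80 percent power loss and 30 percent follow up loss". The sample size is 22. No test or success cut-off is named for the primary endpoint.

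**The concern.** The one-dose set fixes who is in the denominator. It does not say what value a patient takes when week-24 status was not observed, and the literal definition gives an undesirable value for death: no radiological progression, hence controlled. One patient could then be a PFS event and a primary-endpoint success.

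In a randomised trial a poor scoring rule is at least shared by both arms. Here the observed rate is set against a fixed 50%, so each patient moved between controlled, not controlled and excluded shifts the result directly. Unless the rule is written down first, it will be chosen with the outcomes in view.

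The one-cycle set in Appendix 1 works in the same direction. If it were applied to the primary endpoint, patients who die or leave within the first 42 days would drop out of the denominator, and these are likely to be early failures.

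**Working it through.** **1. How the text classifies each case at week 24**

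| Patient | Primary endpoint | PFS |
|---|---|---|
| Dies before week 24, no RECIST progression | Controlled, if read literally | Event |
| Clinical progression, imaging continued, week-24 scan obtained | Classified by the scan | Classified by the scan |
| Clinical progression, no week-24 scan | Not stated | Progression or death if later documented; otherwise censored |
| Clinical progression, new therapy before week 24 | Not stated | Censored at last tamoxifen date |
| Leaves early for another reason, no week-24 scan | Not stated | No specific rule |
| Treated for less than one cycle | In the set (Statistical plan); outside it (Appendix 1) | In the set (Statistical plan) |

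**2. The plan's own figure.** Inputs from the Sample Size Calculation: p0 = 0.50, p1 = 0.70, two-sided alpha 10% (z = 1.645), power 80% (z = 0.842), loss 30%.

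n = [(1.645 × √(0.5 × 0.5) + 0.842 × √(0.7 × 0.3)) / 0.20]² = 36.5, so 37 before loss, and 37/0.7 = 52.9, so 53 after it. The stated 22 is not reproduced. That is a separate finding; below, 22 is taken as given.

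**3. Cut-off (assumption).** I take an exact binomial test with 5% in the upper tail, half of the two-sided 10%. With 2²² = 4,194,304:

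- P(X ≥ 15 | 22, 0.5) = 280,600 / 4,194,304 = 0.067
- P(X ≥ 16 | 22, 0.5) = 110,056 / 4,194,304 = 0.026

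The smallest passing count is therefore 16/22.

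**4. Effect of two unscanned patients (illustrative data).** 15 controlled, 5 progressed, 2 without a week-24 scan:

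| Treatment of the two | Result | One-sided p | Outcome |
|---|---|---|---|
| Controlled | 17/22 | 35,443 / 4,194,304 = 0.008 | Passes |
| Excluded | 15/20 | 21,700 / 1,048,576 = 0.021 | Passes |
| Not controlled | 15/22 | 0.067 | Fails |

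One patient can be enough, since 16/22 passes and 15/22 does not. The point does not depend on the 5% tail. With 10% in the upper tail the cut-off is 15/22 (p = 0.067). Then 13 controlled plus 2 unscanned passes at 15/22 but fails at 13/20 (p = 0.132) and 13/22 (p = 0.262).

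**5. How often two such patients would decide the trial.** Suppose 20 patients are classified with a true rate of 70%, and two are not. At cut-off 16 the two decide the result when the 20 contain 14 or 15 controlled: 0.192 + 0.179 = 0.37. At cut-off 15 the figure is 0.36.

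**6. Cost of counting missing as not controlled.** True rate 70%, share q missing at random; the controlled probability becomes 0.70 × (1 − q):

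| q | Controlled probability | P(X ≥ 16 of 22) |
|---|---|---|
| 0 | 0.70 | 49% |
| 10% (assumed) | 0.63 | 24% |
| 20% (assumed) | 0.56 | 8.4% |

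If the missing patients are instead excluded, and the cut-off is recalculated for each remaining number, the chance of success is 48% at q = 10% and 44% at q = 20%. The unwritten choice is thus worth about 24 and 36 percentage points.

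**The case against.** The best defence is that the plan is not silent. For clinical progression it lets imaging continue after tamoxifen stops, and Appendix 1 asks for every effort to document objective progression. A patient scanned at week 24 is classifiable whatever happened to treatment. Intention to treat fixes the denominator. For death the literal definition does give an answer. The figures above also rest on an assumed cut-off, a constructed dataset and assumed missing shares.

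Much of this stands, and it rules out several stronger readings:

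- A reader might infer that the plan has no provision at all for death, clinical progression or new therapy. It does not support that. Death is classified, though inconsistently with PFS. For clinical progression the gap is limited to a scan that is not obtained, or new therapy started first.
- A reader might infer that study imaging always ends at discontinuation. The follow-up section and the Appendix 1 note say otherwise, although the former only permits continued imaging.
- A reader might take the 30% allowance as the expected share of missing week-24 scans. The plan calls it follow-up loss and does not equate the two.
- A reader might see the two windows (3 days either side in Table 1, 5 days for imaging) as a serious contradiction. They can be read as a visit window and an imaging window. This is a minor point to reconcile.
- A reader might conclude that the 50% null was built under a different definition. The plan describes it only as a placebo-arm result, so this cannot be judged either way.

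The instructions to keep imaging govern data collection. They do not score a patient who has died or has no reading, and they do not resolve the conflict between one dose and one cycle.

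**Conclusion.** The concern holds in a limited form. Followed literally, the primary definition counts a death before week 24 without RECIST progression as disease control, in conflict with PFS. It leaves a treated patient with no week-24 scan unscored. Appendix 1 contradicts the one-dose set. These rules can produce a wrong result, so this is more than missing detail.

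The size is one or two patients: two unscanned patients move the illustrative result between p = 0.008 and p = 0.067, across the assumed threshold. That reversals are possible follows from n = 22 and the 50% null and holds at either cut-off examined. How likely they are depends on the number of such patients, which the documents do not give. The shortfall of 22 against the stated design inputs is a separate matter, though a small sample makes this gap more consequential.

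**What to change.** 1. Define control as alive and without RECIST 1.1 progression at week 24, so that death before week 24 counts as not controlled, consistent with PFS.
2. Use the one-dose set of the Statistical plan as the denominator, and align Appendix 1 with it.
3. Before analysis, fix one primary rule for a patient with no week-24 RECIST reading, including after clinical progression or new therapy: either not controlled, or a Kaplan-Meier estimate at week 24. Report the other as a sensitivity analysis. The first is conservative; the second assumes that censoring is uninformative, which is doubtful after clinical progression. Use the post-discontinuation imaging already in the protocol to keep such cases few. State the cut-off and the power under the chosen rule.
4. Secondary: for PFS, censor at the last evaluable scan before new therapy rather than at the last tamoxifen date, which can discard scans made between the two. Add a sensitivity analysis that counts clinical progression followed by new therapy as an event.
5. Minor: reconcile the visit and imaging windows for the week-24 scan.

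The cost is mostly wording. The real price is a less favourable rate: if missing counts as not controlled, the chance of reaching 16/22 at a true 70% falls from 49% to 24% with 10% missing and to 8.4% with 20%. The 49% starting point comes from the sample size, not from this change.

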Even rarer in the literature is the role of antiestrogen therapies as a form of control of this neoplasia. Case reports point to antiproliferative activity of tamoxifen in patients with NET and, in some cases, patients presenting more than 12 months of disease control.¹¹ Reports of control of carcinoid syndrome and even regression of associated retroperitoneal fibrosis have also been described.^{12,13,14} However, the only study to assess the activity of tamoxifen in neuroendocrine tumors dates back to 1984. Sixteen patients were evaluated clinical benefit in only 19 percent of cases and no radiological response. However, in this study, no patient was previously selected for HR tumor expression or degree of differentiation, which we believe limited benefit in disease control.¹⁵

Therefore, based on the premise that there is a need for research and treatment strategies for this rare neoplasm; there is clear therapeutic embezzlement in the SUS due to the high cost of the treatments approved in the country for this neoplasia; NET are tumors that may present positivity to estrogen and / or progesterone receptors; evidence points to the possibility of antiproliferative effect using hormonal therapy, we propose a phase II study of tamoxifen for patients with well differentiated NET and positive for HR, estrogen and / or progesterone expression.

Hypotheses:

Primary: Tamoxifen, an estrogen receptor agonist, exerts antitumor action in patients with well differentiated NET and positive for the expression of HR, estrogen and / or progesterone.

Secondary:

(1) Tamoxifen will promote reduced levels of chromogranin A and / or specific hormones in biochemically active tumors;

(2) The toxicity profile of tamoxifen will be compatible with the toxicity profile described in the literature.

Purposes:

Primary: To evaluate the efficacy of tamoxifen in patients with well-differentiated NETs, with HR, estrogen and / or progesterone expression, and progression.

Secondary: (1) Evaluate progression-free survival; (2) Evaluate biochemical response; (3) objective response rate; (4) disease control rate according to HR expression intensity and primary site; (5) toxicities

Exploratory:

(1) To evaluate variation of intensity and number of sites capturing PET-CT gallium-68 with tamoxifen;

(2) Document the presence of circulating tumor cells (CTC) and possible diagnostic role, such as liquid biopsy.

Outcomes:

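### Biochemical response counts one unconfirmed 30% fall at any visit, and its denominator does not match the hypothesis; without a control arm, chance falls could make up a non-trivial share

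*Combined protocol and SAP*

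**What the plan says.** - **Definition.** Outcomes, Secondary (2): "Biochemical response will be defined by at least 30 percent drop in the marker". The marker is "chromogranin and / or specific hormone". The fall may occur at any time on treatment and is measured against the pre-treatment value or values. The definition gives no confirmatory sample, minimum duration, raised-baseline condition, denominator or rule for markers that disagree.
- **Hypothesis.** Hypotheses, Secondary (1) expects "reduced levels of chromogranin A and / or specific hormones in biochemically active tumors".
- **Sampling.** Study design, (2) Efficacy: markers are measured "at the baseline and every 12 weeks until progression". Table 1 shows one baseline sample, then weeks 12, 24, 36 and 48. Chromogranin A is measured in everyone; the second marker applies to "specific hormones in cases of functioning NET".
- **Analysis set.** Statistical plan: "Patients receiving at least one dose of tamoxifen will be evaluated for toxicity and efficacy". No rule specific to biochemical response is given.
- **Entry.** The inclusion criteria require no raised marker and expressly admit non-functioning tumours under watchful waiting.
- **Contrast.** Appendix 1 requires complete and partial radiological responses to be confirmed at least 4 weeks later.

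**The concern.** The rule takes the best result over all visits, and over two markers where both are measured. Each extra look or marker adds a chance of crossing the threshold without any drug effect. The rate therefore depends partly on how long a patient is followed and whether the tumour is functioning. A single-arm trial has no comparison group to show how many such falls would occur anyway.

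The population is a second problem. A treated patient with a normal but fluctuating chromogranin A can count as a responder, while one with nothing to reduce can still sit in the denominator. The first raises the rate and the second lowers it, and the documents do not allow a net direction to be stated. Either way, the rate does not answer the hypothesis about biochemically active tumours.

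**Working it through.** The plan gives no expected or null rate for biochemical response, so there is no stated figure to reproduce. The check asks how often the rule is met when the drug does nothing.

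**Inputs from the documents.** Threshold: ratio to baseline of 0.70 or less. One baseline sample and four on-treatment samples in the first year (Table 1). N = 22 and a null disease control rate of 50% at 6 months (Sample Size Calculation).

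**Assumed inputs.** Within-patient CV of 10% to 30%, log-normal variation, independent visits, and independent markers where there are two.

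**One look, by formula.** The log-scale SD is σ = √ln(1 + CV²). Baseline and follow-up both vary, so P(fall ≥ 30%) = Φ(ln 0.7 / (σ√2)). At CV 20%, σ = √ln 1.04 = 0.198. Then ln 0.7 / (σ√2) = −0.357 / 0.280 = −1.27, giving 10.1%. Simulation gave 10.2%.

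**Several looks, by simulation (400,000 patients, shared baseline, no drug effect).** For sampling that stops at progression, 50% control at 24 weeks with constant hazard means √0.5 = 70.7% remain controlled per 12-week interval; the sample at the progression visit is counted. Percentage meeting the rule:

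| Assumed CV | One marker, 1 look | One marker, 4 looks | 4 looks, stopping at progression | 4 looks, marker rising 10% per 12 weeks | Two markers, 4 looks | One marker, 4 looks, two consecutive falls |
|---|---|---|---|---|---|---|
| 10% | 0.6 | 2.0 | 1.3 | 0.1 | 3.9 | 0.1 |
| 15% | 4.5 | 13.2 | 9.2 | 2.0 | 24.7 | 2.4 |
| 20% | 10.2 | 26.2 | 18.9 | 7.9 | 45.6 | 6.8 |
| 25% | 15.3 | 36.3 | 26.9 | 15.5 | 59.3 | 11.4 |
| 30% | 19.4 | 43.7 | 33.1 | 22.9 | 68.2 | 15.7 |

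Four looks instead of one multiply the chance rate by 2.25 (43.7/19.4, CV 30%) to 3.3 (2.0/0.6, CV 10%).

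**In patients.** At CV 20%, 22 × 0.262 = 5.8 chance responders with four samples each, and 22 × 0.189 = 4.2 if sampling stops at progression. At CV 10% the figures are 22 × 0.020 = 0.4 and 22 × 0.013 = 0.3.

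**What remains after the fix.** Selecting on one raised baseline adds regression to the mean. At CV 20% with four samples, the confirmed rate goes from about 7% to 8.5% or 9.8%, taking true levels centred on the upper limit with an assumed log-SD of 1.0 or 0.5.

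**The case against.** The case against is largely about size, and much of it stands.

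- **Noise alone gives a sizeable response rate.** A reader might infer this, but the documents do not support it. They give no CV or assay precision, and at CV 10% the one-marker rate is only 2%.
- **The four-look figures are an upper scenario.** They need every patient to reach week 48 with a flat marker. Patients enter with progressing disease and sampling ends at progression, so the lower columns are at least as relevant.
- **The two-marker rates do not describe the whole trial.** They apply only to functioning tumours, whose number is unknown, and positive correlation between markers would lower them.
- **Counting all patients is not an explicit instruction for this endpoint.** It follows from reading the outcome with the Statistical plan, while the hypothesis points to a narrower group. The fair description is a mismatch over the denominator.
- **The baseline may not be single.** The wording allows more than one pre-treatment value, although Table 1 schedules one. Averaging two would lower the four-look rate at CV 20% from 26.2% to 21.7%.
- **Little rests on it formally.** No test or threshold is attached to this endpoint, and an isolated marker rise does not count as progression.

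None of this removes the defect. The rule still takes the best unconfirmed value over repeated looks, no control arm calibrates the result, and the rate still fails to match its hypothesis.

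**Conclusion.** The point holds in moderated form. The absence of confirmation and the mismatch between hypothesis and denominator can be read directly from the text and need no assumed CV. The number of chance responses does: under assumed CVs of 10% to 30%, one marker and no drug effect, it runs from about 2% to 44% with four samples, or 1% to 33% if sampling stops at progression under the null rate. It is negligible at the bottom of that range and large at the top. The figures also rest on log-normal, independent visit-to-visit variation. The consequence is limited to interpreting a secondary, descriptive endpoint; the primary result is not affected. The wording should be corrected because this rate is the plan's measure for the first secondary hypothesis.

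**What to change.** Define biochemical response for each marker separately: a fall of at least 30% from baseline, present at two consecutive scheduled 12-weekly samples, among patients whose baseline value of that marker is above the laboratory upper limit. Give chromogranin A and the specific hormone their own denominators. Keep the any-visit rate as a descriptive extra, labelled unconfirmed.

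The change is to wording only and uses samples already planned. Its costs are:

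- Patients who progress or stop before a second sample cannot be confirmed. Count them as non-responders and report their number. Under the null rate with constant hazard, 1 − √0.5 = 29% would progress by week 12.
- No response can be confirmed before week 24, so the endpoint partly overlaps with disease control at 24 weeks.
- Denominators will be smaller than 22 if some patients have no raised marker.
- Some noise and regression to the mean remain, about 8 to 10% at CV 20% with four samples. The confirmed rate also still depends on follow-up: before baseline selection, about 3% with two samples against 7% with four at that CV.

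### The hypothesis of reduced marker levels has no analysis that can answer it: the only marker outcome is a described 30% response rate with no reference rate

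*Combined protocol and SAP*

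**What the plan says.** The protocol's Hypotheses section states secondary hypothesis (1) as "Tamoxifen will promote reduced levels of chromogranin A and / or specific hormones in biochemically active tumors". This is a directional claim about level, limited to biochemically active tumours. That subset is not defined further.

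Under Purposes, the matching entry reads "2) Evaluate biochemical response".

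Under Outcomes, secondary outcome (2) reads "Biochemical response will be defined by at least 30 percent drop in the marker (chromogranin and / or specific hormone", and the fall counts "at any time of treatment in relation to pre-treatment value (s".

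Under Study design, item (2) Efficacy, the markers are measured "at the baseline and every 12 weeks until progression". Table 1 schedules them alongside imaging.

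The Statistical plan names no marker analysis. What covers it is the general sentence "Descriptive statistics will be used to report the results of categorical and continuous variables". For the exploratory PET-CT outcome, in contrast, the plan is specific: "The analyzes of intensity of uptake intensity to PET-CT gallium-68 will be with paired T-test".

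**The concern.** The hypothesis is about whether levels go down. The outcome is the share of patients passing a threshold. The two could be linked if the plan said what share to expect without a drug effect, but it does not. The primary outcome has such a reference ("we considered the disease control rate H0 at 6 months of 50 percent"); the marker outcome has none, and the trial has no control arm to supply one.

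Followed as written, the trial would report a response percentage, and readers could not tell from it whether marker levels fell on average. One of the two secondary hypotheses would go unanswered although the values needed are collected. An exploratory imaging measure taken before treatment and at week 12 would receive a full-scale paired analysis, while the marker named in a hypothesis would not.

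**Working it through.** **The plan's own figure.** There is none to reproduce. The documents give no marker SD, expected fall, reference rate, significance level or count of biochemically active patients. The sample size of 22 was derived for disease control at 6 months. Everything below rests on assumptions, shown as ranges.

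**Step 1. Share crossing 30% with no average change, one visit.** Assume ln(week 12 / baseline) is normal with mean 0 and standard deviation SD. A fall of at least 30% means a ratio of 0.7 or less, so the share is Φ(ln 0.7 / SD), with ln 0.7 = −0.357.

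- SD 0.3: Φ(−1.19) = 0.117
- SD 0.5: Φ(−0.71) = 0.238
- SD 0.7: Φ(−0.51) = 0.305

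In 22 patients that is 22 × 0.117 = 2.6 to 22 × 0.305 = 6.7 chance responders at a single visit.

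**Step 2. The any-time rule.** Simulating the best of four on-treatment visits (weeks 12, 24, 36 and 48), with no true change, independent variation of each measurement and a shared baseline, the chance share is 29% at SD 0.3 and 50% at SD 0.5. An observed response rate in this range could therefore occur with no reduction in level.

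**Step 3. Does a continuous analysis have more power?** Both tests are one-sided 5%. The t-test on the log ratio has noncentrality √n × [−ln(1 − fall)] / SD. The cut is an exact binomial test of the 30% responder count. It is given the true chance rate from Step 1 as its null, which is generous because the plan states no such rate. Every patient is assumed to shift by the same average amount.

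Worked case, n = 22, SD 0.5, fall 20%:

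- Noncentrality: 4.69 × 0.223 / 0.5 = 2.09, giving 65% power.
- Responder rate: Φ((ln 0.7 − ln 0.8) / 0.5) = Φ(−0.27) = 0.395, against a null of 0.238.
- The exact test rejects at 10 or more responders. Its actual size is 2.1% and its power 36%. Randomised to exactly 5% (matched size), power is 49%.

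| n | SD | Fall | t-test | Exact cut | Cut, matched size | Gap at matched size |
|---|---|---|---|---|---|---|
| 22 | 0.3 | 15% | 79% | 52% | 56% | 23 |
| 22 | 0.3 | 20% | 96% | 78% | 80% | 16 |
| 22 | 0.5 | 20% | 65% | 36% | 49% | 16 |
| 22 | 0.7 | 20% | 42% | 31% | 32% | 10 |
| 22 | 0.3 | 40% | 100% | 100% | 100% | 0 |
| 22 | 0.8 | 10% | 15% | 8% | 12% | 3 |
| 15 | 0.3 | 20% | 86% | 58% | 66% | 20 |
| 15 | 0.5 | 20% | 50% | 37% | 39% | 11 |
| 15 | 0.7 | 20% | 32% | 13% | 26% | 6 |

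Gaps are differences of the rounded percentages. The rows with n = 15 reflect the plan's 30% loss to follow-up (22 × 0.7 = 15.4) or a biochemically active subset of that size. Over a wider grid of 90 scenarios (n 10 to 22, SD 0.3 to 0.8, fall 10% to 40%), the matched-size gap is under 10 points in about half.

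**Step 4. Two checks that shrink or reverse the gap.**

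- *Any-time rule as written.* Four visits, correlation 0.5 between log ratios, no dropout, true chance rate given, n = 22, fall 20%, matched size: 94% for the cut against 96% for the t-test at SD 0.3, and 59% against 65% at SD 0.5. The gap is 2 to 6 points.
- *Only a minority respond.* If 30% of patients halve their marker and the rest do not change, with n = 22 and SD 0.3, the t-test has 70% power and the exact cut 82%. At SD 0.5 the two are about equal at matched size, both near 48%.

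**The case against.** The strongest reply is that purpose (2) speaks of biochemical response, which the yes/no outcome serves directly, and that a secondary outcome in a 22-patient trial may reasonably just be described. The first part is right about the purpose, but hypothesis (1) is worded as a change in level and still has no matching analysis.

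A reader might infer that cutting at 30% costs a fixed amount of power, say 10 to 30 points. The documents do not support that. No marker test is planned, so there is no planned power to lose. Part of the raw gap comes from the coarseness of the exact binomial test, not from the cut, and the two checks in Step 4 show that the gain can be small or reverse. Nor does the gap close only where both tests are near 100%: it is also small where both have little power.

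A reader might also infer that smaller falls are thrown away. They are left out of the defined outcome only. The values are collected and may be described as continuous variables.

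A further objection stands. A ratio of 1 is not a control. Patients enter with recent radiological progression, so untreated markers need not stay flat, and patients chosen for a raised baseline will tend to regress towards the mean. The ratio estimates change and does not attribute it to tamoxifen. The 30% rate shares this limit.

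**Conclusion.** The point holds as a mismatch between hypothesis and analysis. Hypothesis (1) concerns levels in biochemically active tumours. The single defined outcome is a response percentage with no reference rate, test or interval, and it cannot show whether levels fell. Chance alone would put about 12% to 31% of patients over the line at one visit for an assumed SD of 0.3 to 0.7, and more under the any-time rule.

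The power argument is secondary and conditional. If the shift is common to all patients, a continuous analysis usually does better than a single-visit cut, by 0 to about 23 points at matched size under the assumed inputs. The reason to change is that the level analysis answers the stated hypothesis. The primary outcome is not affected.

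**What to change.** In Outcomes, secondary (2), and in the Statistical plan, add as the analysis of hypothesis (1):

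- **Measure:** the within-patient log ratio of chromogranin A, week 12 to baseline.
- **Patients:** those with biochemically active tumours, defined in advance, for example as a marker above the laboratory's upper limit at baseline.
- **Report:** the geometric mean ratio with a confidence interval, and a paired t-test or Wilcoxon signed-rank test. State how many patients have no week-12 value.
- **Specific hormone:** the same analysis in functioning tumours.
- **Response rate:** keep the 30% outcome as a descriptive companion.
- **Interpretation:** say that the ratio shows change from baseline, including natural course and regression to the mean, and is not by itself evidence of a drug effect.

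The cost is a few lines of text and one more analysis in a small sample. No extra samples, visits or patients are needed. It should be written in before the marker data are analysed, since the same analysis added later would be post hoc.
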